Idiopathic Parkinson's Disease of moderate severity, Hoehn & Yahr Stage 2-4, age >50, usual (carbohydrate predominant) diet at baseline. A total of 32 PD patients will be recruited predominantly from the Parkinson's Clinic at NIH and local sites given necessity of three visits to facilitate randomization and baseline data acquisition. Recruitment will continue as per power analysis for Timed Up & Go (TUG).

Phase:	1
Description of Sites/Facilities	Enrollment will occur at Screening Visit, NIH Clinical Center Outpatient Clinic 5 (OP5). Admission will occur at NIH Clinical Center Metabolic Unit, 7SW.
Enrolling Participants:	Unit, 7SW.
Description of Study Intervention:	The study intervention is randomization to MCT-KD (ketogenic diet with 80% energy from lipids including Liquigen® (KetoCal) comprising 25% of the daily lipid energy divided twice daily or typical, standard American diet (SAD) x 6 days, followed by 2 weeks ketogenic diet in both groups at home. The proposed diets are isocaloric and have the same ratio of protein (10-15% daily energy) with similar mealtime boluses to limit differences in L-DOPA absorption. Daily activity and exercise plans will be individualized upon admission including use of stationary bike, aiming to maintain baseline levels. Diet with MCT oil will begin on hospital day 2

[figure not shown]
Abbreviated Title: Feasibility and efficacy of ketogenic diet in Parkinson’s Disease

Version Date: 04/19/2021

and be provided to both groups at outpatient day 1 Both diets will be double-blinded (combination of shakes and similar appearing snacks). MCT-KD will feature reduced carbohydrate intake of 5-10% daily energy requirement calculated in the Metabolic Unit. Safety monitoring will be performed by IMM.

Study Duration: 9 months
Participant Duration: 3 weeks

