1.3 SCHEDULE OF ACTIVITIES (SOA)

Procedures	Screening/ enrollment *	Day 1 (pre- intervention)	Day 2 (diet started)	D 3	D 4	D 5	D 6	D 7	W 3 (post)
Fill out intake form and determine eligibility	X								
Pregnancy test**	X								
Informed consent	X								
Randomization to Ketogenic Diet or Usual Diet group, stratified 2-factor covariate	X								
anthropomorphic measures (height, weight, abdominal circumference)	X							X	X
Vital signs, including orthostatic (exploratory outcome)	X	X	X	X	X	X	X	X	X
History and Physical Exam	X	X							
Focused Neurologic Exam	X	X							X
Bioelectric Impedance (BIA)	X								X
MOCA	X								
Screening BMP (to establish eGFR), hepatic panel, lipid panel, A1C, beta-HCG if female < age 60	X								

Abbreviated Title: Tolerability and efficacy of ketogenic diet in Parkinson's Disease

Version Date: 04/19/2021

Procedures	Screening	Day 1	Day 2	Day 3	Day 4	Day 5	Day 6	Day 7 / Post	W 3 (post)
UPDRS part 3	X	X	X	X	X	X	X	X	X
Total UPDRS	X								X
Hoehn & Yahr Stage	X								
Electrocardiogram (ECG)	X*	*(If ECG service is unable during screening, may be performed on Day 1 prior to initiation of diet)							
metabolic labs (A1c, insulin, CRP, apolipoprotein panel, HOMA-IR, cortisol, TSH, T3, free T4), BDNF (exploratory outcome), lipid panel (day 7, week 3), A1c (week 3 only)		X						X	X
Non Motor Severity Scale (NMSS) (exploratory outcome)	X								X
PDQ-39 questionnaire (exploratory outcome)	X								X
Resting heart rate variability (2-10 min)		X	X	X	X	X	X	X	X

Abbreviated Title: Tolerability and efficacy of ketogenic diet in Parkinson's Disease

Version Date: 04/19/2021

Procedures	Screening	Day 1	Day 2	Day 3	Day 4	Day 5	Day 6	Day 7 / Post	W 3 (post)
(exploratory outcome)									
Cardiovascular testing – Valsalva maneuver, deep breathing (exploratory outcome)		X						X	X
Timed up and Go (TUG) AM fasting (secondary outcome)	X	X	X	X	X	X	X	X	X
Simple reaction time (SRT) daily (exploratory outcome)		X	X	X	X	X	X	X	X
9-hole pegboard test (9-HPT) daily (exploratory outcome)		X	X	X	X	X	X	X	X
daily journal of ON/OFF and keto-induction symptoms, (Likert scales) and mood (exploratory outcome)		X	X	X	X	X	X	X	X
EEG spectral analysis and connectivity analysis (phase lag index) days 1, 7 (exploratory outcome)		X						X	X
Respiratory Metabolic Cart quotient (pCO ₂ , :pO ₂) for resting and energy expenditure	X								X
BMP, magnesium		X		X	X	X	X	***	

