Abbreviated Title: Tolerability and efficacy of ketogenic diet in Parkinson's Disease**Version Date:** 04/19/2021

POG glc checks		X	X	X	X	X	X	X	
Beta-OHB level twice daily, except once on day 7****		X	X	X	X	X	X	X	X**** *
Procedures	Screening	Day 1	Day 2	Day 3	Day 4	Day 5	Day 6	Day 7 / Post	W 3 (post)
Plasma dopamine twice daily		X	X	X					
Continuous glucose monitoring (Precision Libre Pro)		X	X	X	X	X	X	X	
n-back working memory test daily (exploratory outcome)		X	X	X	X	X	X	X	X
Stroop word color interference test daily (exploratory outcome)		X	X	X	X	X	X	X	X
MN and PQ keyboard tasks		X	X	X	X	X	X	X	X
Safety monitor (telephone interview) survey 2-4 weeks post-study completion									X
Depression screening tool: Geriatric Depression Scale (GDS)	X							X	X
Gastrointestinal motility / symptoms diary (daily days 1-7)		X	X	X	X	X	X	X	

Abbreviated Title: Tolerability and efficacy of ketogenic diet in Parkinson’s Disease

Version Date: 04/19/2021

Gastrointestinal Symptom Rating Scale	X	X						X	X
Exit Survey acceptability of ketogenic diet									X
Tracking diet via unscheduled calls*****	X								X
*No Day 0 (7 days of baseline diet and history, then Day 1 is first day of admission) **women of childbearing potential ***repeat BMP and magnesium on days 6 and 7 if abnormal in prior days ****check beta-OHB in fasted state at week 3 visit ***** To occur during week between screening visit/enrollment and day 1 of admission and during 2 weeks after day 7. See Section 4.1 for details.									

Abbreviated Title: Tolerability and efficacy of ketogenic diet in Parkinson's Disease

Version Date: 04/19/2021

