Overview of Trial Flow and Events. Figure 1 highlights MCT-KD trial flow and events. We propose a screening enrollment of 1-2 participants per week for total of 32 participants. Upon meeting study criteria and consent, participants are asked to provide one week baseline diet and activity/exercise intake, and then be admitted to NIH CC for a one week study intervention assessing ketosis and symptom outcomes, safety monitoring and potential biomarkers of the diet on Parkinson's EEG and BDNF levels. During admission and discharge, communication will be maintained with participants regarding the requested outpatient portion, in which participants are provided meal plans to continue (or in the case of standard diet participants, begin) a standard ketogenic diet, with MCT oil in the home. The outpatient diet will be given as recommended meals and instructions to be reachable via telephone for twice weekly unscheduled calls from NIH CC Nutrition staff to populate diet adherence using diet tracking linked to study investigator's account. Additionally, study nutritionist / investigator (not involved in study rating) will perform unscheduled twice weekly phone calls to obtain post-screening baseline diet (one week) and outpatient KD intervention adherence assessment (two weeks). Participants will then be asked to return for a follow-up visit in NIH CC OP5 two weeks after discharge date. If the appointment date varies from two weeks for any reason, the same visit and measurements will occur, but visits will be demarcated separately for statistical analysis.

Abbreviated Title: Tolerability and efficacy of ketogenic diet in Parkinson's Disease

Version Date: 04/19/2021

Screening procedure: Following recruitment, potential subjects will be pre-screened by telephone, in person, or via email communication according to the inclusion / exclusion criteria, discussion of the scope of the study and study design, expected potential benefits and side effects. If the potential candidate meets the study eligibility criteria, a screening visit will be scheduled at NIH CC outpatient clinic. The estimated duration of the screening visit is 4 hours, and may be spread over 2 separate days if necessary. Upon registration, an order will be submitted for metabolic tracking (PCO₂:PO₂ gas exchange) for calculation of daily resting energy expenditure.

Informed consent will be obtained prior to any tests or procedures being conducted at the screening visit.

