There will be daily monitoring performed by metabolic unit staff and communicated to PI if concern, in turn discussing with independent medical monitor (IMM) and possibly unblinding AI if additional care required such as stopping the intervention, transfer to ICU. There will be no modification to the diets as outlined, to facilitate maintaining blinding and primary and secondary objectives of feasibility and ketosis ascertainment, respectively. There will be weekly meetings by investigators if any adverse events occurred as per Policy 801 (Refer to Section 8.4 for descriptions).

Abbreviated Title: Tolerability and efficacy of ketogenic diet in Parkinson's Disease

Version Date: 04/19/2021

Intervention side effects will be identified by the study LIP who is monitoring the patient during the admission and has daily contact with the participant. With blood glucose monitoring during the study, the nurses will contact study investigators for blood glucose value < 70 mg/dL. The hospital protocols are triggered for BG <40mg/dL that involve sending sample to NIH CC lab, including contacting study investigators for emergent care. For blood glucose 40-70, there will be the following procedure: if asymptomatic and fully alert, 1 cup juice / crackers, recheck in 30 minutes, repeat as necessary. If symptomatic (such as light-headedness, headache, nausea) / mental status lethargy, provide juice / crackers and contact study investigators for possible IV D50 administration.

The literature on safety of the ketogenic diet in adults in clinical trials is robust, including several trials in Parkinson's disease (Krikorian et al 2019, Phillips et al 2018, Vanitallie et al 2005) . The majority of these trials were conducted in the outpatient setting and adverse events were quite rare and typically minor in severity. Similarly, MCT powder/oil as a supplement to accelerate ketogenesis is reported to be safe in Alzheimer's Disease patients (Reger et al, 2004) as well as healthy volunteers (Harvey et al, 2018). Participants will be provided with contact information for the study team and asked to report any concerns, problems or new symptoms. During the 2-week outpatient phase, telephone monitoring may also occur as needed.

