1 STATISTICAL CONSIDERATIONS

9.1 STATISTICAL HYPOTHESIS

Primary hypothesis:

Nutritional ketosis supplemented by MCT oil is feasible within a Parkinson Disease cohort as defined by an acceptable retention rate and outpatient adherence.

Primary outcome: Feasibility of nutritional ketosis(ketogenic diet with 80% lipid including MCT oil, 10-15% protein, 5-10% carbohydrate), in Parkinson Disease cohort defined as a composite outcome meeting all of the following criteria: recruitment target of 32 or as per interim power analysis defined in Section 9.4.6; retention rate > 80% at study end; adherence to ketogenic diet in the outpatient portion defined as mean carbohydrate energy intake <10%, and intervention is acceptable to all participants by Likert scale \geq 2/4 of likelihood of using this therapy in the future and effectiveness in symptom reduction, from all study participants at 3 weeks.

Secondary hypothesis:

Abbreviated Title: Tolerability and efficacy of ketogenic diet in Parkinson's Disease

Version Date: 04/19/2021

Nutritional induced ketosis (NK) increases mobility based on TUG score in a Parkinson Disease cohort at 7 days compared to usual diet (35% lipid, 10-15% protein, 50-55% carbohydrate). Secondary outcome: timed Up & Go test (TUG score) at study day 7 (fastest of three trials)

$H_0: \mu_1 = \mu_2$, where μ_1 and μ_2 are the population means for the NK diet group and usual diet group respectively vs. $H_1: \mu_1 \neq \mu_2$.

Exploratory hypotheses:

Hypothesis A: Nutritional ketosis improves PD symptomatology in cognition (improved attention, recall, and executive function, and motor function akinesia and tremor within six days, as assessed by: Stroop word-color interference latency (executive function), n-back recall task (attention and working memory), simple reaction time (akinesia); fingertap speed and rhythm MN and PQ keyboard tasks (fine motor), and autonomic function (heart rate variability at rest and with deep breathing / Valsalva Maneuver tests)

Hypothesis B: The mechanism of symptomatic reduction of NK in PD is both augmented mitochondrial metabolism (direct, rapid) and augmented neurotransmitter and growth factor synthesis (indirect, delayed), especially GABA and dopamine, as assessed by resting state EEG spectral power, phase coherence, and M1 waveform normalization. Accordingly, effect sizes for exploratory outcomes will be greater at 3 weeks than 7 days.

Exploratory outcomes daily (days 1-7), week 3

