ON/OFF time (daily subjective worksheets), keto-induction symptoms (daily worksheets or self-report), UPDRS-III motor score, MN and PQ keyboard tasks, simple and complex reaction time, 9-hole pegboard test, 3-back recall, Stroop word color interference and latency, tremor amplitude, heart rate variability heart rate variability (SDNN, pNN50, rMSSD, power spectral analysis).

Exploratory outcomes day 1, 7, and week 3:

Valsalva Maneuver and deep breathing cardiovagal tests), plasma BDNF, Geriatric Depression Scale (GDS), EEG sensorimotor spectral power (Hall et al, 2014) and M1 waveform peak:trough asymmetry (Voytek and Cole, 2017).

As an effect of the intervention at three weeks, there is expected to be decrease in EEG beta power on the more affected hemisphere clinically, relating to attenuation of pathologic pallidal GABA efferents to a greater extent than at 7 days or baseline. Similar trends are anticipated for attenuation of M1 waveform asymmetry, reduction in UPDRS total and subtotal scores, decreased latencies and total time of motor task performance tests, improved accuracy and speed of cognitive tasks, and increase in plasma BDNF and heart rate variability measures. The effect on depression symptoms is unclear but reduction is proposed.

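### The control arm first takes the ketogenic diet with MCT oil at home, and about 14 days pass there with no scheduled GI diary, electrolyte test or active adverse-event query

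*Combined protocol and SAP*

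**What the plan says.** The synopsis (1.1) has MCT oil start on hospital day 2 in the MCT-KD arm and "be provided to both groups at outpatient day 1". Section 6.1.1 describes home meal plans with which participants continue, "or in the case of standard diet participants, begin) a standard ketogenic diet, with MCT oil in the home". The return visit is two weeks after discharge.

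The provisions that bear on side effects in those two weeks are:

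- **GI diary.** The schedule (1.3) lists "Gastrointestinal motility / symptoms diary (daily days 1-7") and has no week-3 mark; section 4.1 gives the same days.
- **Keto-induction journal.** The row in 1.3, "daily journal of ON/OFF and keto-induction symptoms, (Likert scales) and mood (exploratory outcome"), is marked on days 1-7 and at week 3. Section 9.1 puts "keto-induction symptoms (daily worksheets or self-report") under the heading "Exploratory outcomes daily (days 1-7), week 3". Sections 4.1, 8.2.3 and 8.4.4 call the survey or worksheets daily and give no last day.
- **BMP/magnesium.** Testing is inpatient only in 1.3, 8.2.3 and 8.4.3.1, and the week-3 cell in 1.3 is empty.
- **Calls.** Section 6.4 describes two unannounced calls a week to take a 24-hour diet recall, with the data used for adherence.
- **Safety contact.** Section 8.3 states that "Intervention side effects will be identified by the study LIP who is monitoring the patient during the admission". For the home phase it says "During the 2-week outpatient phase, telephone monitoring may also occur as needed", and it asks participants to report problems or new symptoms to the study team.

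**The concern.** Section 4.1 describes a phase 1 feasibility and tolerability study. Section 4.2 names the tolerability of MCT oil in this population as a question to answer, and calls home feasibility the key part of the trial. For half the planned sample, first exposure to the diet and the oil happens entirely at home, which is where scheduled capture is thinnest.

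Two of the plan's own provisions lean on data that this arm will not routinely supply:

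- **The 6.3 safety rule.** It is triggered by sodium below 135, potassium below 3.4, magnesium below 1.0, bicarbonate below 22, or vomiting. It runs through Metabolic Unit staff and the Independent Medical Monitor (IMM). At home, no scheduled test can reveal the laboratory triggers, and vomiting surfaces only if the participant mentions it.
- **The 8.4.4 recording rule.** It requires onset and duration for every episode of an intermittent event, which is hard to reconstruct from memory up to two weeks later.

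Section 2.3.1 also relies on electrolyte monitoring. For hypertensive or diabetic participants specifically, it relies on frequent blood-pressure and glucose checks so that medication can be reduced.

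**Working it through.** No figure in the plan needs to be reproduced. The check counts what is scheduled after first ketogenic exposure and before the week-3 visit, by arm.

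Inputs: 16 participants per group (9.2); MCT-KD diet on days 2-7, which is 6 days (1.1, 6.1.1); home phase of 2 × 7 = 14 days (6.1.1); assessment days from 1.3, 4.1, 8.2.3, 8.4.3.1 and 9.1.

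| Scheduled item | MCT-KD arm (exposed from day 2) | Control arm (exposed from outpatient day 1) |
|---|---|---|
| GI diary days | 6 (days 2-7) | 0 of 14 |
| BMP/Mg panels per person | 4 (days 3-6 in 1.3; days 2-5 in 8.4.3.1) or 5 (days 2-6 in 8.2.3), plus conditional repeats | 0 |
| Keto-induction entries, reading 1.3 and 9.1 literally | 6 | 0 |
| Keto-induction entries, if daily includes the home weeks | 6 + 14 = 20 | 14 |
| Staff assessment for side effects | daily during admission (8.3) | none scheduled; telephone contact as needed |

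Totals, as upper limits because some participants may decline or stop the home diet:

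- GI diary days on first exposure: 16 × 6 = 96 in the MCT-KD arm, against 0 of 16 × 14 = 224 home days in the control arm.
- BMP/Mg panels on the diet: 16 × 4 = 64 to 16 × 5 = 80, against 0.
- Planned home calls that could carry adverse-event questions: 2 per week × 2 weeks = 4 per participant, so 4 × 16 = 64 in the control arm and 4 × 32 = 128 overall. Section 6.1.1 mentions calls by Nutrition staff and, additionally, calls by a non-rating nutritionist or investigator. If these are separate sets, the counts double to 8 per participant, 128 and 256.

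The open-ended wording in 8.2.3 covers the GI survey as well. For that form, however, both 1.3 and 4.1 fix days 1-7, so the diary limit is much clearer than the limit on the keto-induction survey.

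What reaches the control arm at week 3 is one journal entry, the GSRS, vital signs including orthostatic measurements, the neurologic examination, UPDRS, NMSS and metabolic labs (with one glucose value per 8.2.3). BMP/magnesium is not listed. The safety-monitor telephone interview comes 2-4 weeks after study completion, outside the home phase.

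**The case against.** The strongest reply is that the grid in 1.3 is not exhaustive. It has no column for the pre-admission home week, yet 4.1 and 8.2.3 call for symptom self-report and continuous glucose monitoring then. The keto-induction survey is online, usable at home and described as daily, and 8.4.4 makes its worksheets the tool for soliciting adverse events. This stands as far as it goes. A reader might infer that the survey stops at day 7, but the documents do not settle that. They leave an end date missing. The argument does not reach the GI diary or BMP/magnesium.

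A second reply is that safeguards remain: participant-initiated reporting, a duty to document every on-study adverse event, a symptom interview and examination at discontinuation (7.1), recorded withdrawal reasons (7.2) and the week-3 assessments. An event mentioned during a diet call must be recorded. This also stands. A reader might infer that the home phase has no safety monitoring, and the documents contradict that.

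Third, Table 1 reports that early symptoms in an earlier PD trial were more frequent in ketogenic weeks 1-4. The control arm's week-3 visit falls at the end of its second ketogenic week, so symptoms persisting then will be seen. Only effects that resolve sooner depend on recall or self-report.

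Fourth, lighter home monitoring is defensible. Section 8.3 notes that most earlier trials were outpatient, with few and mostly minor events, and the eligibility criteria exclude high-risk patients. That supports not mandating extra blood tests. It is weaker as a reason to omit symptom questions from calls already being made, since MCT oil is new to this population.

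**Conclusion.** The point holds as a gap in scheduled, active ascertainment. For up to 16 of 32 participants, the first 14 or so days on MCT-KD have 0 GI diary days, 0 BMP/Mg panels and no planned adverse-event query. The other arm has 6 diary days and 4 to 5 panels after its first exposure. Keto-induction capture in the control arm is anywhere from 0 to 14 entries per person before week 3, depending on how the word daily is read. The counts assume full recruitment and that every control participant takes up the home diet.

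A reader might infer that the main results are compromised, but the documents do not support that. The composite rests on recruitment, retention, carbohydrate intake and the exit survey, none of which uses these forms. The TUG comparison is made on day 7, before the control arm changes diet. No adverse-event comparison is planned (9.4.4 is not applicable), so no planned test is biased. Nor can a number of missed events be derived: the GI rates quoted in 2.3.1 come from a different population and dose, and self-reported events would still be recorded.

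What is lost is detail on early, transient side effects at first exposure in half the sample, on a question that the trial sets itself. Severity is minor to moderate.

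**What to change.** 1. Add brief adverse-event items to the twice-weekly home calls in both arms: GI symptoms including vomiting, dizziness, worsening of PD symptoms and, in diabetic or hypertensive participants, symptoms of low glucose or low blood pressure. Relay positive answers to the non-rating PI and the IMM under the 6.3 rule. Keep them from raters, because induction symptoms at home could hint at the inpatient arm.
2. State in 1.3 and 8.4.4 that the existing online keto-induction survey and the GI diary run through the two home weeks, with a last day.
3. Report symptoms and adverse events by diet actually eaten and by segment. Count the control arm's days 2-7 as standard diet and its home days as first MCT-KD exposure.
4. Leave any added BMP/magnesium test to the sponsor and the IMM.

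The cost is a protocol amendment, a few questions in 128 calls (256 if 6.1.1 describes two sets), and two short forms on up to 32 × 14 = 448 participant-days. No new visit, blood draw, staff or change in sample size is needed. The downside is a small added burden while retention and acceptability are primary criteria. If that weighs heavily, item 1 alone gives an active query about twice a week.

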8.4 ADVERSE EVENTS AND SERIOUS ADVERSE EVENTS

8.4.1 Definition of Adverse Event

Adverse event means any untoward medical occurrence associated with the use of an intervention in humans, whether or not considered intervention-related (21 CFR 312.32 (a)).

